- After study day 56, adverse events should only be reported if they are unexpected or fatal regardless of attribution. All serious adverse events. Reporting of such events should include the investigator's assessment as to whether the event should be attributed to any of the HCT procedure itself, GVHD, or its treatment. An event may be attributable to all, some, or one of these categories.
- Abnormal laboratory values or test results constitute adverse events only if they induce clinical signs or symptoms or require therapy and otherwise meet the criteria for a reportable adverse event as defined above. They are to be captured under the signs, symptoms or diagnoses associated with them.

- All serious adverse event reporting will cease if patient has relapse or second transplant.

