### 10.2.2 Serious Adverse Event

An adverse event is considered “serious” if it results in any of the following outcomes:

- Death
- A life-threatening adverse event  
An adverse event is considered ‘life-threatening’ if, in the view of either the investigator, its occurrence places the patient or subject at immediate risk of death. It does not include an adverse event that, had it occurred in a more severe form, might have caused death.
- Inpatient hospitalization or prolongation of existing hospitalization for  $\geq 24$  hours.
- A persistent or significant incapacity or substantial disruption of the ability to conduct normal life functions
- A congenital anomaly/birth defect
- Important medical event  
Any event that may not result in death, be life-threatening, or require hospitalization may be considered serious when, based upon appropriate medical judgment, they may jeopardize the patient and may require medical or surgical intervention to prevent one of the outcomes listed in this definition of “Serious Adverse Event”. Examples of such medical events include allergic bronchospasm requiring intensive treatment in an emergency room or at home; convulsions that do not result in inpatient hospitalization or the development of drug dependency or drug abuse.

As additional guidance, preplanned hospitalizations or procedures for preexisting conditions that are already recorded in the patient’s medical history at the time of study enrollment should not be considered SAEs.

**The development of steroid-refractory GVHD at any time from study entry to study day 100 will be considered an SAE for the purposes of this study.**

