#### SAE Reporting

	DCC Reports SAE to:		
	DSMB	Single IRB (NMDP)	Consortium
Note: Sites report these SAEs to DCC from patient consent to study day 56			
All SAEs; ✓ Expected or Unexpected ✓ Not Related, Unlikely, Possible, Probable, or Definite	With scheduled submissions	In summary fashion at the time of IRB continuing review	Monthly
Note: Sites report these SAEs to DCC for events occurring after 56 days			
SAEs – ✓ Unexpected ✓ Probable or Definite	5 days from knowledge  AND	Within 10 working days after the investigator becomes aware of the event	Monthly

	With scheduled submissions		
Note: Sites report these SAEs to DCC for events occurring at any time on study			
SAEs – ✓ All deaths not meeting criteria in above two categories	With scheduled submissions	Within 10 working days if the death meets the criteria for an unanticipated problem as defined in Section 10.5	Monthly

10.4.1 The Principal Investigator must be notified within 3 business day of study team's knowledge of any event meeting the criteria and definition per this protocol in section 10.1 of a serious adverse event, occurring during the study.

10.4.2 The investigator must report all events meeting the criteria and definition of a serious adverse event that are unexpected and possibly related (definite, probable or possible to study treatment administration) to the local IRB as per local IRB policy.

10.4.3 All reportable Serious Adverse Events will be reported using the Serious Adverse Event form within 3 days of first awareness of the event to the MAGIC Data Coordinating Center. A copy of the form should be sent to the MAGIC Coordinator via email to [[contact]](mailto:[contact]).

The MAGIC Data Coordinating Center will disseminate information regarding serious adverse events to the participating sites within 3 days of review of the information by the PI or designee if the event(s) is believed to be related (i.e. probably or definitely) to the study treatment. All other Serious Adverse Events will be discussed on monthly webinars held with all participating centers.

The Principal Investigator will be responsible for reporting of events to the FDA and supporters, as appropriate and defined in the regulations under 21 CFR 312.32.

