### Steroid-refractory GVHD:

We expect a rapid steroid taper to be safe for ultra-low risk patients given the high response rates and very low NRM observed in our preliminary data from patients treated with standard steroid doses. The primary risk to patients is the possibility that a rapid taper of steroids will result in GVHD that is non-responsive even to higher doses of steroids. In order to protect study subjects we have designed a stopping rule that will terminate the trial early if a rapid taper leads to an unacceptable incidence of steroid-refractory GVHD. Our preliminary data show that the incidence of steroid-refractory GVHD by day 100 of treatment using the definition in section 9.1.3 in pediatric patients with low risk (Minnesota standard risk/Ann Arbor 1) GVHD is 15%.

We will monitor the number of cases of steroid-refractory GVHD by day 100 in the entire study population and accrual will be halted if there is sufficient evidence that the rate of steroid refractory GVHD exceeds the acceptable target rate of 15% by more than 20% (35% unacceptable rate). If the cumulative number of patients that experience treatment failure is greater than the associated boundary value  $b_k$  listed in the table below, among the  $k$  patients enrolled in the trial, then accrual will be halted for safety considerations. Specifically, if more than 4 of the first 11 patients or more than 5 of the first 15, etc. develop steroid refractory GVHD, the trial will be halted for safety considerations.

Maximum # of Patients, $k$	Up to 11	12-15	16-19	20-23	24-27	28-32	33-36	37-41	42-46	47-50
Boundary, $b_k$	4	5	6	7	8	9	10	11	12	13

The operating characteristics of this stopping rule are as follows:

	True Steroid Refractory Rate		
	15%	30%	35%
Probability of Early Stopping	0.05	0.75	0.92

Using these boundaries, if the true steroid refractory rate is 15%, 30%, or 35%, the probability of stopping the trial early is 0.05, 0.76, and 0.92 respectively.

All the stopping rules were computed using the `toxbdry` function in R and calculations of this function are based on methods described in Chapter 12 of Jennison and Turnbull and in the illustrative paper by Ivanova, Qaquish and Schell. The boundary crossing probabilities under

the acceptable and unacceptable toxicity rates are 0.05 and 0.90 respectively and the boundaries are calculated starting from 10th patient.

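### The SAE cut-off at relapse or second transplant in section 10.2.1 contradicts the rules that require reporting of all deaths and of steroid-refractory GVHD to day 100

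*Combined protocol and SAP*

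**What the plan says.** The cut-off is the last bullet of section 10.2.1: "All serious adverse event reporting will cease if patient has relapse or second transplant". No event type is exempted.

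Four other provisions point the other way:

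- **Section 10.4, SAE reporting table.** The last row has sites report to the DCC "All deaths not meeting criteria in above two categories", and its heading says this is "for events occurring at any time on study". The DCC passes these deaths to the DSMB with scheduled submissions.
- **Section 10.2.1, earlier bullet.** After day 56, "adverse events should only be reported if they are unexpected or fatal regardless of attribution".
- **Section 10.2.2.** "The development of steroid-refractory GVHD at any time from study entry to study day 100 will be considered an SAE".
- **Section 10.6.** "We will monitor the number of cases of steroid-refractory GVHD by day 100 in the entire study population". The boundary is applied as patients accrue: the trial halts "if more than 4 of the first 11 patients or more than 5 of the first 15, etc. develop steroid refractory GVHD".

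Relapse and second transplant are not among the off-study reasons in section 7.8. Section 7.7 follows every child for one year, or to death or withdrawal of consent if earlier.

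**The concern.** A child who relapses stays on study and stays among the k enrolled patients of the stopping rule, while the SAE route for that child's later events is closed. If the child then dies, 10.2.1 says to file nothing and the 10.4 table says to file a report. If the child develops refractory GVHD on day 60, 10.2.2 and 10.6 treat it as an SAE and a countable event, while 10.2.1 suppresses the SAE form.

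At stake are the DSMB's record of deaths and the only numerical safety boundary in the protocol. If post-relapse refractory cases did not reach the count, those children would stay in the denominator without being able to add to the numerator, and the rule would halt less often than section 10.6 states. The loss might not be random: exclusion criterion 5.2.3 recognises that relapse can require withdrawal of immune suppression or donor leukocyte infusion.

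**Working it through.** **1. The rules for a child after relapse or second transplant**

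| Event | Section 10.2.1 cut-off | Other rule |
|---|---|---|
| Death | No SAE report | 10.4 table: report at any time; 10.2.1 earlier bullet: fatal events after day 56 reportable |
| Refractory GVHD to day 100 | No SAE report | 10.2.2: is an SAE; 10.6: counted in all patients |

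No text says which rule prevails.

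**2. What other routes still capture**

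- Section 13.2 requires eCRF data for every section 9.1 endpoint. These include steroid-refractory GVHD (9.1.3) and NRM (9.1.8).
- Table 2 schedules GVHD staging and review of GVHD drugs at visits through day 90, with steroid dose collected to day 90.
- Table 2 records survival and relapse status at days 180 and 365.
- Table 2, footnote 8, collects staging at the first flare.

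Gaps that remain:

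- **Days 91-100.** The rule runs to day 100, but scheduled staging and drug review stop at day 90. The window of 7 days either side puts that visit between day 83 (90 − 7) and day 97 (90 + 7). After it, only an SAE form or a first-flare record would capture a new refractory case, and a child who has already had a first flare has only the SAE form. Footnote 4 adds weekly staging for co-enrolled patients, but to day 100 after transplant, which comes before study day 100.
- **Timing.** Section 10.4.3 sets 3 days for an SAE form. No deadline is given for the eCRF endpoint data. A death after relapse could first surface as survival status at day 180 or 365.
- **Source of the count.** Section 10.6 does not say whether the number of refractory cases comes from SAE forms or from endpoint data.

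**3. The stated operating characteristics**

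Inputs, all from section 10.6: b_k = 4 (k up to 11), 5 (12-15), 6 (16-19), 7 (20-23), 8 (24-27), 9 (28-32), 10 (33-36), 11 (37-41), 12 (42-46), 13 (47-50); halt when the count exceeds b_k; first look at patient 10. The design contrast is a rate that "exceeds the acceptable target rate of 15% by more than 20% (35% unacceptable rate").

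Let a_k(x) be the probability that the trial is still running after k patients with x events. Then a_0(0) = 1 and

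a_k(x) = (1 − p)·a_{k−1}(x) + p·a_{k−1}(x − 1),

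with all x > b_k removed as halted from k = 10 on. P(halt) = 1 − Σ a_50(x).

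| True rate p | Computed | Stated |
|---|---|---|
| 15% | 0.051 | 0.05 |
| 30% | 0.762 | 0.76 (text), 0.75 (table) |
| 35% | 0.922 | 0.92 |

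The plan's figures reproduce. They assume that every refractory case is counted.

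**4. Illustration of a loss**

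The documents give no relapse or second-transplant rate to day 100 and no share of refractory cases that follow either event. Assume that a share m of refractory cases never reaches the rule by any route, so that p becomes p(1 − m).

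| m (assumed) | 35% becomes | P(halt) | 30% becomes | P(halt) |
|---|---|---|---|---|
| 0 | 35.0% | 0.922 | 30.0% | 0.762 |
| 2.5% | 34.1% | 0.903 | 29.3% | 0.727 |
| 5% | 33.3% | 0.880 | 28.5% | 0.690 |
| 10% | 31.5% | 0.823 | 27.0% | 0.608 |

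**The case against.** The strongest reply is that nothing need be lost. Section 10.6 names no data source, the eCRFs cover refractory GVHD, relapsed children remain on study, and section 15.0 has the DCC collate all data and safety reports for the monitoring committee. A site might also treat the specific rules on deaths as overriding the general cut-off. Further, failure to respond by day 28 is itself refractory under 9.1.3, so many cases may be settled before most relapses. The stopping rule asks whether the taper causes refractory GVHD, and an event after withdrawal of immune suppression may have another cause. Limiting SAE noise is a stated aim of 10.2.1. Section 10.6 also lets the investigators, the DSMC or the IRB recommend stopping.

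Much of this stands. A reader might infer that these deaths and refractory cases would be wholly unreported. The documents do not support that: they would be unreported as SAEs, and most would still be collected by other means. A reader might also infer that the IRB should receive all deaths. In the deaths row it is notified within 10 working days only if the death meets the unanticipated-problem criteria. Nor can one say what proportion of deaths would be missed, because no post-relapse mortality is given.

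The contradiction itself is not answered, nor is the gap after the day-90 visit. If post-relapse events were meant to be excluded as not attributable to the taper, 10.6 would need to say so. It says the entire study population.

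**Conclusion.** The concern holds as a contradiction in the reporting rules. Followed literally, 10.2.1 withholds SAE reports of deaths and of refractory GVHD to day 100 that 10.4, 10.2.2 and 10.6 call for. This conclusion needs no assumption. The practical exposure is late knowledge of these events, plus days 91-100, where no scheduled staging or drug review backs up the SAE form.

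The effect on the stopping rule cannot be sized from the documents. The fall from 0.92 to 0.90, 0.88 or 0.82 at a true 35% rate is illustrative. It requires that 2.5%, 5% or 10% of refractory cases follow relapse or second transplant and are captured by no other route. It is not evidence that the rule's stated properties are wrong. The correction is worth making because it is cheap and concerns safety reporting in a paediatric trial.

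**What to change.** Amend the last bullet of section 10.2.1 along these lines: SAE reporting ceases at relapse or second transplant, except that (a) deaths continue to be reported as the section 10.4 table sets out, and (b) steroid-refractory GVHD continues to be reported through study day 100 and counted under section 10.6.

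Flag events after relapse or second transplant in the DSMB listing so that attribution can be judged. Exception (b) also makes the duty to day 100 explicit, which the post-day-56 row of the 10.4 table, limited to unexpected SAEs of probable or definite relation, does not.

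The cost is one sentence and a few extra SAE forms for children already followed to one year. Treatment, endpoints, boundaries and sample size are unchanged.

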### 10.2.2 Serious Adverse Event

An adverse event is considered “serious” if it results in any of the following outcomes:

- Death
- A life-threatening adverse event  
An adverse event is considered ‘life-threatening’ if, in the view of either the investigator, its occurrence places the patient or subject at immediate risk of death. It does not include an adverse event that, had it occurred in a more severe form, might have caused death.
- Inpatient hospitalization or prolongation of existing hospitalization for  $\geq 24$  hours.
- A persistent or significant incapacity or substantial disruption of the ability to conduct normal life functions
- A congenital anomaly/birth defect
- Important medical event  
Any event that may not result in death, be life-threatening, or require hospitalization may be considered serious when, based upon appropriate medical judgment, they may jeopardize the patient and may require medical or surgical intervention to prevent one of the outcomes listed in this definition of “Serious Adverse Event”. Examples of such medical events include allergic bronchospasm requiring intensive treatment in an emergency room or at home; convulsions that do not result in inpatient hospitalization or the development of drug dependency or drug abuse.

As additional guidance, preplanned hospitalizations or procedures for preexisting conditions that are already recorded in the patient’s medical history at the time of study enrollment should not be considered SAEs.

**The development of steroid-refractory GVHD at any time from study entry to study day 100 will be considered an SAE for the purposes of this study.**

### 10.2.3 Expected Adverse Events

In this protocol, an adverse event (AE) is considered “expected” if it is described in the Package Insert, in published medical literature, in the protocol, or in the informed consent document.

#### 10.2.4 Unexpected Adverse Event

In this protocol, an adverse event (AE) is considered “unexpected” if it is not described in the Package Insert, in published medical literature, in the protocol, or in the informed consent document.

### 10.3 Adverse Event Characteristics

#### 10.3.1 CTCAE Term

(AE description) and grade: The descriptions and grading scales found in the NCI Common Terminology Criteria for Adverse Events (CTCAE) version 5.0 will be utilized for AE reporting. A copy of the CTCAE version 5.0 can be downloaded from the CTEP web site. (<http://ctep.cancer.gov>)

#### 10.3.2 Attribution of the AE

The investigator or co-investigator is responsible for assignment of attribution.

**Definite** – The AE *is clearly related* to the study treatment.

**Probable** – The AE *is likely related* to the study treatment.

**Possible** – The AE *may be related* to the study treatment.

**Unlikely** – The AE *is doubtfully related* to the study treatment.

**Unrelated** – The AE *is clearly NOT related* to the study treatment.

### 10.4 Serious Adverse Event Reporting Guidelines

The Sponsor Investigator will report SAEs to regulatory bodies and to the participating sites in the following manner:

#### SAE Reporting

	DCC Reports SAE to:		
	DSMB	Single IRB (NMDP)	Consortium
Note: Sites report these SAEs to DCC from patient consent to study day 56			
All SAEs; ✓ Expected or Unexpected ✓ Not Related, Unlikely, Possible, Probable, or Definite	With scheduled submissions	In summary fashion at the time of IRB continuing review	Monthly
Note: Sites report these SAEs to DCC for events occurring after 56 days			
SAEs – ✓ Unexpected ✓ Probable or Definite	5 days from knowledge  AND	Within 10 working days after the investigator becomes aware of the event	Monthly

	With scheduled submissions		
Note: Sites report these SAEs to DCC for events occurring at any time on study			
SAEs – ✓ All deaths not meeting criteria in above two categories	With scheduled submissions	Within 10 working days if the death meets the criteria for an unanticipated problem as defined in Section 10.5	Monthly

10.4.1 The Principal Investigator must be notified within 3 business day of study team's knowledge of any event meeting the criteria and definition per this protocol in section 10.1 of a serious adverse event, occurring during the study.

10.4.2 The investigator must report all events meeting the criteria and definition of a serious adverse event that are unexpected and possibly related (definite, probable or possible to study treatment administration) to the local IRB as per local IRB policy.

10.4.3 All reportable Serious Adverse Events will be reported using the Serious Adverse Event form within 3 days of first awareness of the event to the MAGIC Data Coordinating Center. A copy of the form should be sent to the MAGIC Coordinator via email to [[contact]](mailto:[contact]).

The MAGIC Data Coordinating Center will disseminate information regarding serious adverse events to the participating sites within 3 days of review of the information by the PI or designee if the event(s) is believed to be related (i.e. probably or definitely) to the study treatment. All other Serious Adverse Events will be discussed on monthly webinars held with all participating centers.

The Principal Investigator will be responsible for reporting of events to the FDA and supporters, as appropriate and defined in the regulations under 21 CFR 312.32.

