## 10.5 Reporting of Unanticipated Problems

Upon becoming aware of any incident, experience, or outcome (not related to an adverse event) that may represent an unanticipated problem involving risks to subjects or others, the investigator should assess whether the incident, experience, or outcome represents an unanticipated problem. The incident, experience or outcomes are considered unanticipated if it meets all of the following criteria:

1. Unexpected (not previously documented in terms of nature, severity, or frequency);
2. Causally related or possibly related to participation in the study; and
3. Suggests that the research places subjects or others at a greater risk of harm than was previously known or recognized.

If the investigator determines that the incident, experience, or outcome represents an unanticipated problem, the investigator must report it to the MAGIC Data Coordinating Center within 3 days of first awareness of the events, and to the local IRB as per local IRB policy.

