## 10.6 Stopping Rules

The primary risk from a rapid steroid taper is the possibility of steroid-refractory GVHD. We will monitor the study subjects for the development of steroid-refractory GVHD. We will allow continuous accrual on to the study unless a stopping rule is met or the target accrual is reached. The study may also be stopped based on the recommendation of the investigators, the TCI DSMC, or the single IRB.

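### The SAE table gives the DSMB and single IRB prompt notice of unexpected, related events only after day 56, so not during the four-week taper

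*Combined protocol and SAP*

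**What the plan says.** The SAE Reporting table in Section 10.4 has three rows, split by when the event occurs.

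- **Row 1** covers events "from patient consent to study day 56". It takes in all SAEs, expected or unexpected, of any attribution: "Not Related, Unlikely, Possible, Probable, or Definite". The DSMB receives them "With scheduled submissions", and the single IRB receives them "In summary fashion at the time of IRB continuing review".
- **Row 2** covers events after day 56 that are unexpected and probably or definitely related. The DSMB is told 5 days from knowledge and again in the scheduled submission. The single IRB is told "Within 10 working days after the investigator becomes aware of the event".
- **Row 3** applies at any time on study, but only to deaths that do not fall in the first two rows. The DSMB again waits for scheduled submissions. The single IRB hears within 10 working days if the death meets the Section 10.5 criteria for an unanticipated problem.

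Section 7.5 sets protocol therapy at four weeks. Section 10.6 allows continuous accrual and adds: "The study may also be stopped based on the recommendation of the investigators, the TCI DSMC, or the single IRB".

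**The concern.** The expedited timelines begin four weeks after protocol therapy has ended. An unexpected, definitely related SAE on day 60 goes to the DSMB in 5 days. The same event on day 20, with the child on the taper under test, goes with the next routine package, and the single IRB sees it in a summary at continuing review. One would expect the treatment period to be watched at least as closely as follow-up, and the protocol gives no reason for the reverse.

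At stake is whether the two independent bodies named in Section 10.6 can act in time. Section 15.0 makes the TCI DSMC the DSMB of record, with no member connected to the trial, whereas the Protocol Committee consists of site investigators. The only numeric stopping rule concerns steroid-refractory GVHD. For any other unexpected harm from the taper, these bodies depend on being told.

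**Working it through.** The main check is a comparison of texts; the plan states no figure to reproduce.

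**Step 1. Same event, two dates.** Take an SAE that is unexpected and probably or definitely related.

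| Recipient | Consent to day 56 (row 1) | After day 56 (row 2) |
|---|---|---|
| DSMB | next scheduled submission, interval not stated | 5 days from knowledge |
| Single IRB | summary at continuing review | 10 working days (about 14 calendar days) |

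Four weeks of therapy is 28 days, and 28 < 56, so all of the taper lies in the first column.

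**Step 2. Does row 3 help with deaths?** Section 10.2.2 makes death a serious outcome, so a death up to day 56 is already in row 1. Row 3 is limited to deaths outside rows 1 and 2 and therefore does not reach it. Even if its any-time heading is read generously, row 3 gives the DSMB no expedited report. Its faster IRB clause covers only deaths that qualify as unanticipated problems.

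**Step 3. Is there another prompt route to either body before day 56?**

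- 10.4.1: the PI, within 3 business days.
- 10.4.2: the local IRB, per local policy, for unexpected events that are definitely, probably or possibly related.
- 10.4.3: the coordinating center within 3 days; participating sites within 3 days of PI review if probably or definitely related; the FDA under 21 CFR 312.32.
- 10.5: unanticipated problems go to the coordinating center and the local IRB. Its opening sentence concerns an "incident, experience, or outcome (not related to an adverse event) that may represent an unanticipated problem".
- 10.6: a boundary on the count of steroid-refractory GVHD cases, which sets no SAE reporting time.
- 15.0: annual reviews and safety reporting to the single IRB.

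None of these is an expedited report to the DSMB or the single IRB.

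**Step 4. Size (illustration only).** Section 14.2 gives 30 patients a year, or 2.5 a month. It also says that centers will open at different times and that accrual is realistically expected within three years: 50 / 36 = 1.4 a month. Further enrolments before the DSMB is told are rate × delay.

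- 5 days: 1.4 × 5/30 = 0.2; 2.5 × 5/30 = 0.4.
- 3 months (assumed): 50/36 × 3 = 4.2; 2.5 × 3 = 7.5.
- 6 months (assumed): 50/36 × 6 = 8.3; 2.5 × 6 = 15.
- 12 months (assumed): 50/36 × 12 = 16.7; 2.5 × 12 = 30.

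These are upper limits, for an event just after a submission. For the single IRB the wait is up to about 12 months, if the annual review in Section 15.0 is the continuing review.

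**The case against.** The strongest reply is that the main hazard is handled elsewhere. Section 10.6 names steroid-refractory GVHD as the primary risk and monitors it to day 100 with accrual-halting boundaries that do not depend on this table. Because that event is described in the protocol, it is expected under 10.2.3, so earlier row 2 timelines would not expedite it anyway. Section 10.2.1 also justifies lighter adverse event reporting by long experience with steroids and the de-escalation design. All of this stands, and it narrows the point to other unexpected, related SAEs. It does not explain why such events should reach the DSMB faster after treatment than during it.

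A second reply is that the DSMB charter or the single IRB's own policy may require prompt reports. That is possible, but neither is available here, and the protocol's table would still state a different rule.

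Three stronger readings are tempting, and the documents do not support them.

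- A reader might infer that events during the taper go unreported or that nobody can act. The PI, coordinating center, sites, local IRBs and FDA all have routes before day 56. The investigators may also recommend stopping, and site PIs meet monthly.
- A reader might infer from 10.2.4, which calls an event unexpected "if it is not described in the Package Insert, in published medical literature, in the protocol, or in the informed consent document", that almost nothing after transplant would qualify and row 2 would rarely apply. The definition is broad, but nothing in the documents shows how many events it would remove.
- A reader might infer that 10.5 bars deaths from counting as unanticipated problems. The parenthesis stands only in the introductory sentence; the three numbered criteria contain no such exclusion, and row 3 assumes that deaths can qualify. The wording needs reconciling, but it is not a bar.

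**Conclusion.** The point holds as a limited gap. From consent to day 56, including the entire taper, the protocol provides no prompt notice to the DSMB or the single IRB of an unexpected, related SAE, although it does so after day 56. The gap is confined to those two bodies and to events other than steroid-refractory GVHD. No endpoint, analysis or stopping boundary is affected.

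The comparison rests on the table as written and needs no assumption. The enrolment figures do: the DSMB interval is assumed, the accrual rate is given as a range, and the delays are worst cases. Quoting 30 patients alone would combine the longest assumed interval with the faster accrual rate.

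A related inconsistency needs settling at the same time. Row 2 expedites only probable or definite events, while 10.4.2 also counts possible ones as related. As written, possibly related events never get an expedited report to the DSMB or, unless row 3 catches a death, to the single IRB.

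**What to change.** In the Section 10.4 table:

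1. Apply the row 2 timelines (DSMB 5 days; single IRB 10 working days) to unexpected, related SAEs at any time from the start of study treatment. Keep the scheduled and summary routes for all other SAEs to day 56.
2. State one definition of related for that row, reconciling row 2 (probable or definite) with 10.4.2 (which adds possible).
3. Reword row 3 so that its 10-working-day IRB clause also covers deaths up to day 56, and reconcile it with the introductory wording of 10.5, for example by stating that deaths are assessed on the three numbered criteria.

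The expectedness definitions in 10.2.3 and 10.2.4 can stay as they are. The cost is a wording change and a few additional expedited reports. No visits, data items or patients are added.
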